## 1. TITLE OF RESEARCH PROTOCOL

Serological screen and treat trial for *P. vivax*: a proof-of-concept trial in eastern Indonesia

### 3. Study Synopsis

Study title	SEROLOGICAL SCREEN AND TREAT TRIAL FOR P. VIVAX: A PROOF-OF-CONCEPT TRIAL IN EASTERN INDONESIA
Regulatory Status	Investigational – individually randomised phase IIb proof-of-concept trial
Investigational Product and Route	Multi-antigen sero-diagnostic test for measurement of P. vivax antibodies in plasma from finger stick as a means to detect hypnozoite carriers for treatment
Study Objectives	
Primary objective:
 
To determine the efficacy of a Serological Screening and Treatment (SSAT) intervention for the prevention of recurrent P. vivax malaria.
 
Secondary objectives:
 
 
(I) To evaluate the performance of a point-of-care (POC) anti-P. vivax antibody detection test relative to Luminex (MagPix).
 
(II) To evaluate safety of high dose PQ administration in schoolchildren.
 
(III) To evaluate the accuracy of Sahli’s method and Standard G6PD (SD Biosensor Inc., Suwon-si, Gyeonggi-do, Republic of Korea) relative to HemoCue for haemoglobin measurement.
 
(IV) To estimate the sensitivity and specificity of a microscopic diagnosis of malaria by blood sample from skin (ankle) relative to standard finger stick microscopic and PCR.
 
(V) To measure duration of gametocyte in the blood samples of the skin of the ankle and finger prick.
 
(VI) To estimate the sensitivity and specificity of magneto-optical hemozoin detection by Gazelle® (Hemex Health, USA) relative to standard finger stick microscopic and
 

	
PCR.
 
(VII) To analyse hemoglobinopathies in schoolchildren using HemeChip by Gazelle (Hemex Health, USA)
 
Primary study endpoint: the proportional reduction of P. vivax incidence by PCR in children serologically screened relative to those receiving routine care during 9 months of active follow-up.
 
Secondary endpoints:
 
(I) Difference in the time-to recur of P. vivax by PCR in SSAT and control arms.
 
(II) Difference in the number of recurrent P. vivax by PCR in SSAT vs. control arms.
 
(III) Difference in the incidence of recurrent symptomatic P. vivax by LMF in SSAT vs control arms.
 
(IV) Seroconversion rate before and after intervention in SSAT and control arms.
 
(V) Sensitivity and specificity of POC antibody detection test vs. gold standard Luminex assay.
 
(VI) Adverse event (AE) and Severe Adverse Event (SAE) of high dose PQ in schoolchildren.
 
(VII) Hb level in Sahli's method, Standard G6PD (SD Biosensor Inc., ROK), and Gazelle® (Hemex Health, USA), in comparison with HemoCue (HemoCue AB, Angelholm, Sweden).
 
(VIII) Sensitivity and specificity of microscopic examination to detect parasitemia from the shallow skin vasculature of the ankle (light microscopy-skin/LMS) compared to standard microscopic (light microscopy-finger/LMF) and PCR.
 
(IX) Mean duration time of gametocyte in LMS and LMF
 
(X) Sensitivity and specificity of magneto-optical hemozoin detection (MOD) compared to standard malaria detection and PCR.
 
(XI) Hemoglobinopathy rate in schoolchildren

Study Site	Malaka regency, East Nusatenggara province, Indonesia.
Study Duration	January 2020 to January 2021
Number of Participants, Randomisation, and Treatment	
A total of 800 elementary schoolchildren and their households living at Malaka, West Timor.
 
Randomization and Treatment:
 
 
Participants will be randomized into two groups: (1) intervention group (SSAT; n=400) and (2) routine care group (n=400). All participants will be tested for presence of antibodies to a validated panel of P. vivax antigens and
 

	
standard finger stick microscopic.
 
 
• In the SSAT arm at enrollment, only children who are Pv seropositive and/or LMF Pv/Po positive receive supervised high-dose primaquine (1mg/kg for 7 days) regardless of their symptoms. All blood slides will be processed and read directly after blood collection. Then treatment will follow if positive. Sero-positive children, on the other hand, will commence treatment after the result is available (approximately 1 week). Symptomatic or asymptomatic LMF positive for Pf/Pm will be treated according to current national guidelines.
 
• In the control arm at enrollment, only children who are symptomatic and LMF Pv/Po positive will receive supervised high-dose primaquine (1mg/kg for 7 days).
 
• In both arms at every other timepoint, symptomatic LMF positive children will receive treatment in accordance with national guidelines (unsupervised).
 
• In both arms at the final timepoint, LMF will be conducted on all children and if positive will be treated according to national guidelines.
 
• As blood schizontocides, DHA-PP for 3 days will be given according to body weight (national guidelines).
 

Inclusion and Exclusion Criteria
	
Inclusion:
 
 
• resident of study area and attending selected elementary school in Grade 1-5
 
• no evidence of health condition that would interfere with study participation
 
• assent of child and documented parental informed consent
 
 
Exclusion:
 
 
• G6PD deficiency as determined by SD Biosensor quantitative determination of <70% G6PD activity (male: <4 U/g Hb, female: <6 U/g Hb).
 
• Haemoglobin < 9 g/dL
 

Analysis plan and sample size calculation
	
The study is designed to show a superiority of SSAT vs. routine care for the prevention of recurrent P. vivax infections. The primary study endpoint will be the proportion of children with recurrent P. vivax by PCR during 9 months of follow-up. Secondary endpoints include time-to-first P. vivax recurrence as well as incidence of symptomatic

	
P. vivax.
 
SSAT intervention is expected to reduce incidence of P. vivax in comparison to standard care. With the previous prevalence rate of 20%, we will have a power of >90% to detect a significant difference with the sample size of 350 children per group. We will anticipate the exclusion of 15% by recruiting 400 children per group.

Lay Summary
	
This study evaluates an experimental serological diagnostic technique intended to identify people at high risk of having dormant malaria parasites in their liver. The findings will assess the ability of this sero test to identify those carriers.
 
800 children living in eastern Indonesia will be individually randomised to the experimental serologic test or routine care.
 
Children in the serological diagnosis arm will be screened for the presence of antibodies to a previously validated panel of malaria antigens optimized for sensitivity to infection during the prior 9 months. Furthermore, they also will be screened by microscopy. If positive by either test, they will be treated for that malaria infection.
 
Children assigned to routine care will be screened by microscopic examination and treated when they show or have history of symptoms in the last 3 days.
 
After initial screening and treating according to diagnostic technique, all children will be actively followed for 9 months with PCR detection every 4 weeks.
 
During 9 month follow up, all children becoming acutely ill and proven to be positive for malaria by microscopy will be treated, in addition, all asymptomatic children will be treated at the final time point.
 
POC serology test will be performed at baseline and final timepoint on all children in both arms. The results from this POC serology test will not be used to inform diagnosis or treatment in any way at either of the timepoints.
 
None of these blood samples will be collected by venopuncture but instead minimally invasive lancet devices will be used.

Sero-diagnostic test
	
Quantitative measurement of antibody titres to a panel of 8 specially selected P. vivax antigens in study subject plasma samples using a Luminex MAGPIX® bead array system. This testing will be done at the Eijkman Institute in Jakarta. The results will be generated in no

	more than 7 days.
--	-------------------

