### **5.2. Secondary objectives:**

1. To evaluate the performance of a point-of-care (POC) anti-*P. vivax* antibody detection test relative to Luminex (MagPix).
2. To evaluate safety of high dose PQ administration in schoolchildren.
3. To evaluate the accuracy of Sahli's method and Standard G6PD (SD Biosensor Inc., Deogyong-daero, Korea) relative to HemoCue for haemoglobin measurement.

4. To estimate the sensitivity and specificity of a microscopic diagnosis of blood by sample from skin (ankle) relative to standard finger stick microscopic and PCR.
5. To measure duration of gametocyte in the blood samples of the skin of the ankle and finger prick.
6. To estimate the sensitivity and specificity of magneto-optical hemozoin detection by Gazelle® (Hemex Health, USA) relative to standard finger stick microscopic and PCR. To analyse hemoglobinopathies in schoolchildren using HemeChip by Gazelle (Hemex Health, USA)

*Primary endpoint:* the proportional reduction of *P. vivax* incidence by PCR in children serologically screened relative to those receiving routine care during 9 months of active follow-up.

*Secondary endpoints:*

- (I) Difference in the time-to recur of *P. vivax* by PCR in SSAT and control arms.
- (II) Difference in the number of recurrent *P. vivax* by PCR in SSAT vs. control arms.
- (III) Difference in the incidence of recurrent symptomatic *P. vivax* by LMF in SSAT vs control arms.
- (IV) Seroconversion rate before and after intervention in SSAT and control arms.
- (V) Sensitivity and specificity of POC antibody detection test vs. gold standard Luminex assay.
- (VI) Adverse event (AE) and Severe Adverse Event (SAE) of high dose PQ in schoolchildren.
- (VII) Hb level in Sahli's method, Standard G6PD (SD Biosensor Inc., Deogyong-daero, Korea), and Gazelle® (Hemex Health, USA), in comparison with HemoCue (HemoCue AB, Angelholm, Sweden).
- (VIII) Sensitivity and specificity of microscopic examination to detect parasitemia from the shallow skin vasculature of the ankle (light microscopy-skin/LMS) compared to standard microscopic (light microscopy-finger/LMF) and PCR.

- (IX) Mean duration time of gametocyte in LMS and LMF
- (X) Sensitivity and specificity of magneto-optical hemozoin detection (MOD) compared to standard malaria detection and PCR.
- (XI) Sensitivity and specificity of Standard G6PD (SD Biosensor, Inc., Deogyong-daero, Korea Korea) compared to CareStart G6PD RDT (Access Bio. Inc., New Jersey, USA).

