### 6.3. Study design and study overview

The study design is a randomized controlled trial with serological screening and treatment as the intervention. Selected schoolchildren will be allocated into two study arms: (1) serological screening and treatment (SSAT), and (2) routine care as control arm.

At enrolment, in the SSAT arm, individuals found *P. vivax* positive by either serological (Luminex) or Giemsa stained microscopic examination regardless of the symptoms will receive supervised treatment (direct observation) with high dose PQ (daily 1 mg/kg BW) for 7 days ( $P_o=P_v$ ). In the control arm, only symptomatic individuals found *P. vivax* positive by Giemsa stained microscopic examination will receive the same regimen ( $P_o=P_v$ ). In addition, in the treated children of both arms, dihydroartemisinin-piperaquine (DHA-PP) will be given as blood schizontocide according to body weight. All other species (*P. falciparum*, *P. malariae*) found by Giemsa stained microscopic examination will be treated according to national guideline. Serological examination will be performed by Luminex (done at Eijkman, Jakarta) and point-of-care (POC) antibody detection using rapid test on site

Follow up will be performed monthly for 9 months. During this period, 400  $\mu$ L of finger pricked blood samples will be collected from all children in both arms. These samples will be tested for malaria presence by PCR which will be done at EO CRU, Jakarta. However, children with clinical symptoms (body temperature of  $\geq 37.5^\circ\text{C}$  and/or history of fever within 3 days), will be examined by Giemsa stained microscopy on site, and treated if positive (any species) according to national guideline (unsupervised).

At the last follow up, a mass blood survey will be conducted to both arms for *Pv* serological test, LMF, and PCR. Those found positive by LMF for any species will be treated regardless of their symptoms.

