### **6.8. Antimalarial treatment**

Treatment will be provided based on body weight (Appendix B). Blood schizonticide for any species is 3-day DHA-PP (daily dose: 6-10 kg=1/2 tab, 11-17 kg=1 tab, 18-30 kg=1 ½ tab, 31-40 kg=2 tab). For *P. vivax* subjects, the administration of high dose primaquine will be started at the same day of DHA-PP treatment (see Table 2 appendix B for PQ dosage). Meal should be given prior to PQ administration daily. The total dose of PQ should be completed within 10 days as the window period. Subjects who does not complete the dose will be recorded, and still be followed until end of study. Monitoring of Hb level and hemoglobinuria for treated subjects will be done daily before and during treatment by Hb measurement using HemoCue (HemoCue AB, Angelholm, Sweden) and urine test (inspection and urinalysis) in order to detect hemolysis. Primaquine will be stopped if hemolysis

occur, the subject will be observed for daily vital sign, Hb level, and urine until recovery. If worsen, the subject will be referred to the hospital for further management, and given blood transfusion if necessary (Appendix E).

Primaquine for *P. falciparum* will be given as single dose 0.25 mg/kgBW (6-17 kg=1/4 tab, 18-30 kg=1/2 tab, 31-40 kg=3/4 tab). *P. ovale* will be treated as *P. vivax*. Mixed infection with *Pv* will be treated as *Pv*.

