### 8.3. Data analysis

*Plasmodium vivax* incidence is defined as the total number of new genetically distinct *P. vivax* clones per child per detected during the follow up period. The analysis will use the comparison of two incidence rates between SSAT group and control group. For comparison, data will be entered as the number of recurrent *Pv* (numerators) and the total length of time people contributed in the cohort (person-time) as denominators. We will calculate the exact probabilities (Fisher's and Mid-P), the rate ratio with the exact confidence intervals and the measures of the impact of intervention. We will report the 95% of confidence interval for this comparison. Measures of the impact of intervention are computed for the prevented fractions in the exposed and in the population and the preventable fraction in the population.

As secondary endpoints, we will use Kaplan-Meier method to detect differences in the time-to-first recurrence of *Pv* by PCR in SSAT and control arms. The log-rank test is used to detect any difference between the two groups. Cox proportion hazard will be used to measure the effect size.

Multiple recurrences of *P. vivax* infections will be calculated during follow up. Number of events will be calculated, divided by the total length of time people

contributed in the cohort (person-time) as denominators. We will calculate the exact probabilities, rate ratio with the exact confidence intervals, and the measures of the impact of intervention using same tests as above.

Symptomatic recurrent *P. vivax* is defined as LMF positive with fever ( $\geq 37.5^{\circ}\text{C}$ ) or history of fever in the last 3 days during follow up. The same statistical test will be performed to compare both groups.

Difference of seropositivity between the two arms before and after the intervention will be calculated using chi-square test with p value  $< 0.05$  as limit of significance.

Sensitivity, specificity, positive predictive value, and negative predictive value of POC *Pv* antibody rapid test will be reported with Luminex as the golden standard.

Type and number of AE and SAE will recorded, and reported with total length of time people contributed in the cohort (person-time) as denominators.

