**CASE REPORT FORM**

**ID :**

**NAMA:**

**L/P**

**FAMILY SCREENING/SEKOLAH:**

**G6PD:**

**HASIL: *P. FALCIPARUM / P.VIVAX / P. MALARIAE / P. OVALE***

Hari	D-1	D-2	D-3	D-4	D-5	D-6	D-7	D-8	D-9	D-10	D-11	D-12	D-13	D-14
Tanggal														
DHP (jml tablet)														
Primakuin (jml tablet)														
Hb (D-1 sebelum minum obat & D-3)														
Urin (D-1 sebelum minum obat)														
Keluhan														
Alergi														
Pusing														
Sakit kepala														
Bibir kebiruan														
Keluhan di dada														
Mual														
Muntah														
Gangguan napsu makan														
Gangguan Buang Air Besar (BAB)														
Gangguan Buang Air Kecil (BAK)														
Gangguan tidur														
Tanda tangan pasien														
Tanda Tangan Petugas Pengawas Minum Obat														
Tanda Tangan Manajer Site/Wakil

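### The safety endpoint is labelled as adverse events of high-dose primaquine, but nearly every such child also takes DHA-PP on days 1 to 3 and complaints have no marked pre-dose reading

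*Protocol*

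**What the plan says.** The safety objective in Protocol section 5.2 is "To evaluate safety of high dose PQ administration in schoolchildren", and endpoint VI in the Synopsis and in section 5 is "Adverse event (AE) and Severe Adverse Event (SAE) of high dose PQ in schoolchildren". Section 4 says the results are meant to support guidelines for high-dose primaquine in primary health centres.

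The treatment given is a combination. Section 6.3 states that "in the treated children of both arms, dihydroartemisinin-piperaquine (DHA-PP) will be given as blood schizontocide according to body weight". The Synopsis adds "As blood schizontocides, DHA-PP for 3 days will be given according to body weight (national guidelines". Section 6.8 says that "the administration of high dose primaquine will be started at the same day of DHA-PP treatment". The schedule in Appendix H shows DHA-PP on D1 to D3 and primaquine on D1 to D7.

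Section 6.9 defines an adverse event without linking it to a drug and ties routine observation to the seven days of drug administration. Section 8.3 says: "Type and number of AE and SAE will recorded, and reported with total length of time people contributed", with cohort person-time as the denominator.

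The case report form in Appendix J has one column per day from day 1, with rows for tablets of each drug, haemoglobin, urine and a list of complaints, for example "Gangguan napsu makan" (appetite). The haemoglobin and urine rows carry a note that the day-1 value is taken before the drug. The complaint rows carry no such note.

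**The concern.** The endpoint names one drug, while the data come from two drugs started together in children who may already have complaints. Three sources of a recorded complaint cannot be separated: what the child had before the first dose, what DHA-PP causes, and what primaquine causes. In symptomatic slide-positive children, malaria itself adds to the first.

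What is at stake is the use named in section 4. A tolerability figure quoted for high-dose primaquine would carry complaints that primaquine did not cause. Part of this cannot be repaired later: if complaints are not recorded before the first dose, no analysis plan can separate new from existing ones.

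**Working it through.** The protocol gives no figure for this endpoint (no expected rate, precision or test), so there is nothing to reproduce. The check sets the passages side by side and then shows a range.

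**1. Overlap of the two drugs.** DHA-PP runs for 3 days and primaquine for 7, from the same day (Synopsis, section 6.8, Appendix H). Overlap = 3/7 = 43% of primaquine days, including the first dose. There are two exceptions, hence *nearly every* child:
- Seropositive children whose slide shows *P. falciparum*, *P. malariae* or both have seven-day primaquine added on the serology result (Appendix I), so the courses need not overlap.
- Children allergic to DHA-PP receive second-line treatment instead (section 6.9).

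**2. What is known before the first dose.**

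| Item | Pre-dose value stated? |
|---|---|
| Haemoglobin | Yes (section 6.8, Appendix H, case report form) |
| Urine | Yes (same places) |
| Temperature, fever history | At enrolment (section 6.6); about 1 week before dosing for serology-only children (Synopsis) |
| Headache, dizziness, nausea, vomiting, appetite, bowel, sleep | None stated |

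**3. Is there a comparator?** Routine observation follows the drug days (section 6.9). No equivalent observation of untreated children is stated, so the control arm gives no background rate for these complaints.

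**4. How many children.** Eligible schools have 30% to 70% seroprevalence (section 6.2). In the SSAT arm, 400 × 0.30 = 120 to 400 × 0.70 = 280 children would receive high-dose primaquine through serology (105 to 245 if 350 remain after exclusions).

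**5. Illustrative background.** Let b be the chance per child-day of a listed complaint with no drug effect. This is assumed; the documents give no value. The chance of at least one in seven days is 1 − (1 − b)^7.

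| b (assumed) | At least one in 7 days | Of 120 | Of 280 |
|---|---|---|---|
| 0.5% | 3.4% | 4 | 10 |
| 1% | 6.8% | 8 | 19 |
| 2% | 13.2% | 16 | 37 |
| 5% | 30.2% | 36 | 84 |

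**6. How far a ratio depends on assumptions.** With weekly background B and drug effect d, the crude proportion is 1 − (1 − B)(1 − d).
- d = 5%: B = 5% gives 9.8% and B = 20% gives 24.0%, which is 1.95 to 4.8 times d.
- d = 20%: the same B values give 24% and 36%, which is 1.2 to 1.8 times d.

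Both B and d are assumed, so no single inflation factor can be claimed.

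**7. The reported rate.** If events seen in 7 days are divided by the full follow-up (9 months, about 274 days), the rate is diluted by 274/7, or about 39-fold. This works against the excess from background complaints.

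**The case against.** The strongest reply is that a reader might infer the plan charges every complaint to primaquine, and it does not. Section 6.9 defines events without reference to a drug and its stopping criteria speak of antimalarial treatment as a whole; section 8.3 only counts events. Adverse events of the regimen as given also inform a guideline in which a blood schizontocide accompanies primaquine. This stands: the attribution lies in the label of the objective and endpoint, not in an event-by-event rule.

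Other points on that side:
- **Haemolysis.** It has pre-dose haemoglobin and urine. This stands, and the point is confined to subjective complaints.
- **Malaria symptoms.** SSAT children "receive supervised high-dose primaquine (1mg/kg for 7 days) regardless of their symptoms", so symptomatic malaria probably affects a minority there. It affects every control child given high-dose primaquine at enrolment, since symptoms are required. This stands.
- **Direction.** A reader might infer that the reported rate is biased upward. Step 7 shows why that does not follow; only counts and proportions of children are inflated.
- **Size.** A reader might infer a two- to five-fold excess. Step 6 shows that this depends on assuming a small drug effect.
- **Timing on the form.** It does not say whether day-1 complaints are asked before or after dosing. True, but with one cell per day it cannot show both.
- **Left to the analysis plan.** Onset tables can be, since tablets and complaints are logged daily. A reading never taken cannot.
- **Days 4 to 7 as a clean primaquine window.** A reader might want primaquine statements restricted to these days. That would discard early primaquine reactions and would not remove lingering piperaquine effects.

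**Conclusion.** The concern holds for subjective complaints. The label promises primaquine tolerability, but the design yields complaints during a two-drug course, with no stated pre-dose reading and no stated observation of untreated children. Counts and proportions of children with these complaints will include background and DHA-PP effects.

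The size is unknown. The range of 3.4% to 30% of treated children with a complaint from background alone rests wholly on the assumed daily rate of 0.5% to 5%. The documents do not establish the direction of error in the person-time rate, and haemolysis monitoring is outside the point. The endpoint is secondary and descriptive, but the missing reading is cheap to add now and cannot be recovered later.

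**What to change.** 1. Add a pre-dose day-1 entry to the case report form for the existing complaint checklist, and count only new or worsened complaints as adverse events.
2. Rename the endpoint *AEs and SAEs during DHA-PP plus high-dose PQ*, and word the objective to match.
3. As supportive description only, show events by onset on D1 to D3 and from D4 onward, using the daily tablet counts already on the form. Keep all D1 to D3 events in the main safety table.

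The cost is one form column and one table split. The limitation is that the D4-onward table does not isolate primaquine, because piperaquine effects may persist. No dose or clinical rule changes.

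Separately, the form lists haemoglobin on days 1 and 3 and urine on day 1 only, whereas section 6.8 and Appendix H describe daily checks. These places must be reconciled.

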### **8.2. Sample size consideration**

Sample size is calculated based on the difference in the incidence of *P. vivax* infection between the intervention and control arm. The impact of the SSAT intervention is expected to reduce incidence of *P. vivax* in schoolchildren compared to control group. Our study in 2013 found *Pv* prevalence of ~20% by PCR (2). Different effect and sample sizes were simulated using a specific mathematical transmission model (24) and statistical power calculated. With the proposed sample size of 350 children per arm, we will have a power of >90% to detect a significant difference (Figure 3). Assuming 15% exclusion rate, we will recruit 400 children per arm.

**Figure 3. Simulation of various sample size (n=50-500) to detect significant difference in the proportion of infected subjects during follow up period.**

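### The protocol names conflicting primary endpoints (proportion of children, or an incidence whose unit of counting is unsettled), and the >90% power is not clearly tied to the analysis in section 8.3

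*Protocol*

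**What the plan says.** Five places in the protocol bear on the primary endpoint.

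- **Synopsis, analysis plan and sample size row.** "The primary study endpoint will be the proportion of children with recurrent" P. vivax by PCR during 9 months. This is a yes/no outcome per child.
- **Synopsis endpoint list and section 5 (below 5.2).** Both give the proportional reduction of P. vivax "incidence by PCR in children serologically screened relative to those receiving routine care during 9 months of active follow-up".
- **Section 8.3, opening definition.** P. vivax "incidence is defined as the total number of new genetically distinct" P. vivax "clones per child per detected during the follow up period". This is a count of clones.
- **Section 8.3, the comparison itself.** The numerator is the count of recurrent P. vivax, with "the total length of time people contributed in the cohort (person-time) as denominators". The analysis is a rate ratio with exact confidence limits and exact (Fisher and mid-P) probabilities.
- **Section 8.2.** The text opens "Sample size is calculated based on the difference in the incidence of" P. vivax infection. The caption of Figure 3, cited for the >90% power at 350 per arm, describes a simulation "to detect significant difference in the proportion of infected subjects during follow up period".

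Secondary endpoint II is the difference in the number of recurrences. Section 8.3 analyses multiple recurrences over person-time with the same tests as the primary.

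**The concern.** These quantities score the same child differently. A child with one recurrence carrying four new clones counts 1 as a proportion, 1 as a recurrence count and 4 as a clone count. A child with three single-clone recurrences, all new and distinct, counts 1, 3 and 3.

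Three things follow. The effect estimate and its significance can differ by definition, and nothing in the protocol says which governs. If recurrences are the numerator, the primary analysis and secondary endpoint II are the same analysis. And the outcome the synopsis calls primary has no analysis in section 8.3, while the analysis that section does prescribe has no power clearly attached to it.

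This is not detail that can be left to an unseen analysis plan. Whichever version such a plan chose, it would contradict another part of the protocol.

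**Working it through.** **Inputs from the protocol.** 350 children per arm, power >90%, and a P. vivax PCR prevalence of about 20% in 2013 (section 8.2).

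**Assumptions.** Two-sided alpha 0.05, inferred from the 95% interval in section 8.3. A 9-month control proportion of 20%; the protocol gives 20% only as an earlier prevalence. The design effect is not stated and Figure 3 is not shown, so the >90% cannot be reproduced exactly. What can be found is the effect it would need.

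**1. Proportion of children.** Power = Φ{[|p1 − p2| − 1.96·√(2p̄(1−p̄)/n)] / √[(p1(1−p1) + p2(1−p2))/n]}.

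With n = 350, p1 = 0.20, p2 = 0.1114 and p̄ = 0.1557, the two standard errors are 0.02741 and 0.02720. Then (0.0886 − 1.96 × 0.02741)/0.02720 = 1.28, and Φ(1.28) = 0.90. So 90% needs 20% versus 11.1%, a risk ratio of 0.557. At risk ratios of 0.6 and 0.7 the power is 82% and 56%. If the control proportion were 30%, 40% or 50%, risk ratios of 0.65, 0.71 or 0.76 would suffice. The stated >90% is attainable on this scale.

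**2. Clone rate, tested validly.** Same 20% versus 11.14% infected; clones per infected control child 1 + Poisson(λ), λ = 0.5 to 3 (assumption); log rate ratio with robust variance; 6,000 simulated trials per setting.

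| Mean clones per infected child, SSAT relative to control | Rate ratio | Power |
|---|---|---|
| equal | 0.557 | about 80–83% |
| 10% lower | 0.557 × 0.9 = 0.501 | about 92–93% |
| 20% lower | 0.557 × 0.8 = 0.446 | about 98% |

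The test of the proportion stays at about 90% throughout.

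**3. Recurrence rate.** Take event counts whose chance of at least one event is 20% versus 11.14%. If they are Poisson, the mean is −ln(1 − p), giving 0.223 versus 0.118 and a rate ratio of 0.53. If negative binomial with dispersion k, the mean is k[(1 − p)^(−1/k) − 1], giving 0.25 versus 0.125 at k = 1 and 0.281 versus 0.133 at k = 0.5. Power is about 92%, 94% and 96%. If a rate ratio of 0.6 is fixed instead, the rate has 79%, 77% and 74%, against 76%, 70% and 63% for the proportion.

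**4. The planned exact test on clone counts.** An exact rate test treats every clone as an independent event. For a child infected with probability p, the variance-to-mean ratio of the clone count is [(1+λ)² + λ]/(1+λ) − p(1+λ).

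- λ = 0.5: 2.75/1.5 − 0.3 = 1.53. Real type I error 2[1 − Φ(1.96/√1.53)] ≈ 0.11; simulated 0.12.
- λ = 3: 19/4 − 0.8 = 3.95. Real type I error 2[1 − Φ(1.96/√3.95)] ≈ 0.32; simulated 0.31 to 0.32.

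So the error is about 0.12 to 0.32 over the assumed range. A robust variance restores it to about 0.05.

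**The case against.** The best defence is that most of these places form one family. The two endpoint lists agree word for word, and a rate ratio with prevented fractions is a natural way to estimate a proportional reduction in incidence. Section 7.9 says genotyping is used to tell new infections from existing ones, so a new clone may simply be how a recurrence is recognised. On that reading the firm conflict is two-way, between the synopsis analysis-plan sentence (with the Figure 3 caption) and everything else. This largely stands. A reader might infer three wholly incompatible definitions; the text supports a proportion against an incidence rate, with the counting of clones left unclear. What the defence does not settle is whether several new clones in one sample count once or several times.

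A reader might also infer that the >90% belongs only to the proportion, or is wrong. Neither is supported. Section 8.2 opens by basing the sample size on incidence, and only the caption names the proportion. The figure is plausible for a proportion but cannot be verified.

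Finally, a reader might infer that moving to a clone rate costs about ten points of power. That holds only if SSAT lowers the chance of infection but leaves clones per infected child unchanged. A treatment aimed at the source of repeated relapses could plausibly lower both, and then the clone rate has more power than the proportion.

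**Conclusion.** The contradiction stands on current text and needs no assumption: a per-child proportion in one place, a reduction in incidence in others, a clone definition followed by a recurrence numerator in section 8.3, and no analysis of the proportion. Section 8.2 is inconsistent about which metric was powered. The primary result is not fixed by the protocol as written.

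The sizes are illustrative. They rest on a 20% control proportion borrowed from a prevalence, two-sided 0.05, and assumed clone numbers and dispersion. Within those limits power ranges from about 80% to 98% by definition, on either side of the 90% for the proportion, so neither a loss nor a gain can be claimed. The firmer statistical consequence is for validity: if clones are counted, the exact tests named in section 8.3 would reject far more often than 5% under the null.

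**What to change.** Name one primary endpoint, in identical words, in the synopsis endpoint list, the synopsis analysis plan, section 5 and section 8.3, and list the others as secondary.

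The simplest choice that matches the synopsis analysis plan and Figure 3 is the proportion of children with at least one PCR-detected P. vivax recurrence over 9 months. Section 8.3 then needs a matching risk-ratio or two-proportion analysis, and time to first recurrence stays as secondary endpoint I. In section 8.2, give the control proportion, the effect and the alpha behind the >90% on that scale.

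If a recurrence or clone rate is preferred as primary:

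- state whether several new clones in one sample count once or several times;
- separate it from secondary endpoint II;
- replace the exact rate test with one that allows for clustering within a child (negative binomial or robust variance);
- rerun the simulation for that endpoint and restate the power.

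The first route costs wording, one added analysis and a fuller power statement. The second adds one rerun of the existing simulation, whose result may be higher or lower than 90%. Neither changes recruitment or sampling unless the restated power proves inadequate.
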